Study Protocol

Official Title of the study: Effectiveness and safety of Chinese herbal medicine for hepatitis B virus-related acute-on-chronic liver failure: A multi-center, randomized and controlled trial

NCT number: not yet assigned

Date of the document: June 21, 2018

This prospective, multi-center, parallel, centrally randomized controlled trial was designed in accordance with the Consolidated Standards of Reporting Trials (CONSORT) and Standard Protocol Items: Recommendations for Interventional Trials (SPIRIT) guideline, which is led by the principal investigator from 302 military hospital in Beijing, will be carried out from September 2018 and December 2020 among 16 tertiary academic hospitals in China. Patients with hepatitis B virus (HBV) related Acute-on-chronic liver failure (ACLF) will be randomly allocated to the Chinese herbal medicine (CHM) group or the standard medical treatment (SMT) group in a 1:1 ratio. The last patient will be enrolled before August 2019 to make sure the availability of 48 week's survival status by the end of this study. We will decide whether to expand additional institutions to guarantee adequate enrolments after interim assessment of effective participant numbers around December 2018. Patients in the SMT group will receive the standard medical treatment, and patients in the CHM group will receive rhubarb decoction enema for 1 week and CHM for 8 weeks additionally. All patients will be followed at pre-designed time points after 8 weeks' observational period until August 30, 2020 for the primary outcome and secondary outcomes.

The study is consistent with Good Clinical Practice(GCP) guidelines and has been approved by 302 military hospital ethics review committee (2018007D). Written informed consent is requisite to be signed by the patients or the authorized person under the willingness. The privacy and data of all participants will be protected carefully before, during and after the trial.

Patients will be consented and enrolled by co-principal investigators at each institution and managed by care providers including residents, attending physicians and nurses according to the protocol. Most of the patients will be treated in hospital for 8 weeks so clinicians can supervise the administration of CHM, in addition, the policy of reimbursement filed by the lab results at determined time points will boost the regular follow-up of this study.

Diagnostic criteria

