The study will end at once if severe adverse events associated with CHM occurs or sufficient evidence indicates that adding CHM is not superior to the SMT group. Besides, CHM will discontinue and the final status will be censored in the condition of liver transplantation or the onset of liver cancer. Allocated interventions can be changed upon participant's request. All these changes will be recorded and analyzed based on intention-to-treat (ITT).

Intervention

Standard medical treatment

The SMT include a high-calorie diet; nucleoside analogues for HBV DNA-positive patients; sodium restriction, diuretics and paracentesis combined with albumin infusion for ascites; lactulose and L-ornithine aspartate and lactulose for HE and hyper-ammonia; hemostatic treatment for gastrointestinal hemorrhage; antibiotics for infections and renal replacement for HRS and uremic symptoms. CHM formulas, whatever routes of administration, are prohibited in the SMT group.

Chinese herbal medicine formula

There are two kinds of CHM based on traditional Chinese Medicines (TCM) syndromes. The common components of the two CHM formulas include *Artemisiacapillaris* Thunb (30g), *Salvia miltiorrhiza* Bge (30g), *Rhizoma*

Atractylodis Macrocephalae (30g), Rubia cordifolia L (30g), Sieyesbeckiaorientalis L (30g). Additional four components of Paeoniae Radix Rubra (60g), Gardenia jasminoides Ellis (9g), Hedyotis diffusa Willd (30g), Bletilla striata (15g) are involved for excess syndrome, and five other components of Astragalus membranaceus (30g), Radix Pseudostellariae (15g), Radix Aconiti Lateralis Praeparata (10g), Galli Gigeriae Endothelium Corneum (20g), Polygonum cuspidatum Sieb.et Zucc (15g) are involved for deficiency syndrome. All ingredients are manufactured as a Chinese herbal granule in a specific weight ratio to the raw herb (Beijing Kang Rentang Pharmaceutical Co., Ltd, Beijing, China) in accordance with the quality criteria of Chinese pharmacopoeia in 2015. Patients will take one dosage of CHM granule per day for 8 weeks. For patients who cannot take oral medicine can be switched to colon route by the colonic therapy system (IMS-100A produced by Sunny Medical in Beijing China).

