In addition, patients in the CHM group will also receive daily herbal enema of 100 microliter decoction composed by Radix et Rhizoma Rhei Palmati (Dahuang) 30g and Fructus Mume (Wumei) 30g for 7 days expect the following contraindications: (1) severe hemorrhoid, (2) female patients during menstruation, (3) anal stenosis, (4) artificial anal and (5) cardiac disease.

Outcome measurements

Primary outcome

The primary outcome is transplant-free survival at week 12.

Secondary outcomes

Secondary outcomes include (1) transplant-free survival at week 24, (2) the influence on liver function assessed by MELD score (involving levels of serum bilirubin, creatinine, INR and sodium) at week 12, (3) the influence on liver function assessed by Child-Pugh score (involving the serum bilirubin, coagulation function, albumin and the complication of hepatic encephalopathy and ascites) at week 12. (4) quality of life assessed by WHOQOL-BRIEF at week 12 and (5) the incidence of serious complications (including infections, encephalopathy, HRS, and gastrointestinal bleeding) from week 1 to week 24.

Safety outcomes

Primary vital signs, physical examinations, electrocardiogram and some laboratory tests such as routine blood test, urine test, renal function will be assessed before and after treatment to monitor the safety of this study. Furthermore, adverse events are also recorded in a predesigned case report form (CRF) through the whole study period. An independent safety committee will analyze the incidence and severity of adverse events to identify any unexpected adverse events or mortality in the CHM groups.

Other assessed parameters

Epidemiological characteristics, the details of nucleoside/nucleotide analog therapy, family history of liver disease were collected from patient medical record, the level of HBV DNA, endotoxin, and lymphocyte subsets were tested as well as CLIP-C-ACLF score were computed at week 24 and 48. The plasma level of HBV DNA, endotoxin, and cytokines were tested in ADICO clinical laboratories (Shanghai, China) which is blind to the allocation information. Remnant plasma will be stored at -80°C for ancillary studies. Women of childbearing age will undergo pregnancy test for the eligibility.

Sample size

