The randomized subjects who take at least one dose of CHM or SMT constitute the full analysis set (FAS) and those who complete all the visits constitute the per-protocol set (PPS). An efficacy assessment will be analyzed using FAS and PPS based on the principle of ITT. Subjects who have taken the CHM and been evaluated the safety at least once constitute the safety set (SS), which is used for safety evaluation. The statistical analysis will be performed using SAS 9.0 software (SAS Institute, Cary, NC, USA) by independent data management committee who are blind to the interventions.

Comparison of the two groups is conducted for the continuous variables with *t*-test and the categorical variables or rates with the chi-square test. The Kaplan-Meier overall survival curves will be generated and tested by log-rank. Cox proportional hazards regression model will be adopted to determine the prognostic factors associated with transplant-free survival. Multivariate logistic regression analyses will be adopted to explore factors associated with the incidence of liver-related complications. Subgroup analyses will be done based on the diagnostic criteria of Asian Pacific Association for the Study of the Liver (APASL) and European Association for the Study of the Liver (EASL) guideline.

The last observation carried forward approach was used for missing values. The statistical significance is defined as a two-sided $P < 0.05$.

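### The plan does not say which test decides week-12 transplant-free survival, and its log-rank test has no time limit and does not test the week-12 rate

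*Combined protocol and SAP*

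**What the plan says.** All references are to the combined protocol and SAP.

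- *Primary outcome*: "The primary outcome is transplant-free survival at week 12". This is a status at one fixed time.
- *Secondary outcomes*: the only other survival outcome listed is "transplant-free survival at week 24". Overall survival is not listed.
- *Data management and Statistical methods*: the plan will compare "the categorical variables or rates with the chi-square test". It then states: "The Kaplan-Meier overall survival curves will be generated and tested by log-rank". The next sentence applies a Cox model to transplant-free survival, to look for prognostic factors. The section closes with one general threshold: "The statistical significance is defined as a two-sided $P < 0.05". It names no primary analysis, order of testing, alpha split or log-rank horizon.
- Opening section: the enrolment deadline is set "to make sure the availability of 48 week's survival status by the end of this study", and patients are followed "until August 30, 2020 for the primary outcome and secondary outcomes".
- *Criteria for discontinuing or modifying allocated interventions*: "the final status will be censored in the condition of liver transplantation or the onset of liver cancer".
- *Sample size*: the calculation uses 8-week mortality, 30.87% in the control group and a 12-point difference, and names no test.

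**The concern.** Carried out as written, the plan yields at least two P values on survival, a comparison of rates and a log-rank over follow-up. Both are judged at 0.05, and no sentence says which one answers the primary question.

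Two things are at stake. If the choice is made after the results are seen, the 5% level no longer holds. The two tests can also disagree for good reason: deaths after week 12 move the log-rank and leave the week-12 rate unchanged. A disagreement would then have to be settled by argument instead of by the plan.

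The endpoint wording adds to this. A log-rank on overall survival, or one that censors at transplantation, does not count a transplant as a failure. A transplant-free endpoint does.

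**Working it through.** **1. Does the sample size show which test was meant?** Inputs from *Sample size*: 30.87% against 18.87% (taking the 12 points as the expected difference), power 0.80, two-sided 0.05, 10% attrition, stated result 255 per group. With n/(1 − 0.10) for attrition:

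- two proportions, pooled variance: 203, giving 226
- the same with continuity correction: 219, giving 244
- log-rank, Schoenfeld: 98 events, giving 220 per group
- log-rank, Freedman: 103 events, giving 232 per group

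None gives 255, so the figure does not identify the test. It also refers to week 8, not week 12.

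**2. How far past week 12 could the log-rank run?** The opening section starts the trial in September 2018, enrols the last patient before August 2019 and follows patients to 30 August 2020. From 1 August 2019 to that date is 395 days, or 56 weeks. From 1 September 2018 it is 729 days, or 104 weeks. Without a stated cut, much of the log-rank's follow-up lies after week 12.

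**3. False-positive rate if either test may decide.** Trials were simulated with no treatment effect.

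- Week-12 test: z = (p₁ − p₀) / √[p̄(1 − p̄)(1/n₁ + 1/n₀)]
- Log-rank: z = Σ(O − E) / √ΣV, cut at week 12, 24 or 48
- Each rejects if |z| > 1.96. The same event is used in both tests.

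The documents give only 30.87% at week 8, so the later event rates are assumptions:

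- Early plateau: 31%, 33% and 35% at weeks 12, 24 and 48.
- Intermediate: 35%, 40% and 45% at weeks 12, 24 and 48.
- Constant hazard: 1 − 0.6913³ = 67% at week 24 and 1 − 0.6913⁶ = 89% at week 48.

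Either-test rejection, 255 per arm, 40,000 trials per cell:

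| Assumed curve | Log-rank to week 12 | to week 24 | to week 48 |
|---|---|---|---|
| Early plateau | 5.6% | 6.4% | 6.5% |
| Intermediate | 5.6% | 6.8% | 7.1% |
| Constant hazard | 5.7% | 7.9% | 8.7% |

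Alone, the week-12 test rejected in 4.9-5.2% of trials and the log-rank in 4.8-5.1%. At 229 per arm (255 × 0.90 = 229.5), 10,000 trials per cell gave 5.5-5.8% at week 12, 6.3-8.0% at week 24 and 6.6-8.8% at week 48. These agree within simulation error: √(0.07 × 0.93 / 10,000) = 0.26 points. Two independent tests would give 1 − 0.95² = 9.75%. The positive correlation between the tests keeps the figure below that.

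**4. Do the two tests answer the same question?** With 255 per arm and 40,000 trials:

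- Event rates equal at week 12 (35% in both arms), then 40% against 50% at week 48: the 48-week log-rank rejects in 45% of trials, the week-12 test in 4.8%.
- Rates equal at week 12 (35%), but 10% against 20% at week 4: a log-rank cut at week 12 rejects in 6.9%, the week-12 test in 4.9%.

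The first case shows that full follow-up can produce a positive log-rank with no week-12 difference. The second shows that cutting at week 12 narrows the gap but still compares whole curves.

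**5. Endpoint wording side by side.** The outcome section makes transplant a failure. The discontinuation section makes it a censoring event. The log-rank sentence names overall survival, while the Cox sentence that follows names transplant-free survival. The documents give no transplant rate, so the effect of this conflict cannot be sized.

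**The case against.** The best defence is that the plan is clear enough. It has one primary outcome at one time point, a rate at week 12. It sends rates to the chi-square test. The sample size is also built on a difference in rates. On that reading the log-rank only describes the curves, and nothing allows it to replace the week-12 comparison. Most of this stands: chi-square is the natural reading. It remains an inference, because the sentence covers rates in general and the sample size names neither week 12 nor a test.

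A reader might go further the other way and infer that the trial has two co-primary tests, an error rate of 8% or more, or no defined conclusion. The documents do not support that. They fix a single primary outcome and do not say that either test may be claimed. The excess is conditional on a freedom that the plan leaves open but does not grant. Nor is the upper figure typical. It needs a constant hazard, with 89% of patients having an event by week 48. Plateau curves give 6.4-6.5%, and since no horizon is stated, a week-12 cut at about 5-6% is also a possible reading.

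It can also be said that overall survival is a different endpoint, so the two tests do not compete. It may be a different endpoint, but then it is not among the listed outcomes. If the term is loose wording for transplant-free survival, the competition is real. The text does not settle which.

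**Conclusion.** The point holds as a gap in specification. The decisive test for the primary outcome is not named, the log-rank has no horizon and does not test the week-12 rate, and its stated endpoint is not a listed outcome. The censoring of transplantation contradicts a transplant-free endpoint.

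The effect on the error rate is modest and conditional. If either test may be claimed, it is about 5-6% with the log-rank cut at week 12 and about 6.3-8.7% with it run to 24-48 weeks, against about 5% with one named test. This rests on assumed event curves after week 8, one common event definition and no loss to follow-up in the simulated trials. Follow-up beyond 48 weeks was not simulated. The possible disagreement between the tests matters regardless of these figures.

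**What to change.** Before database lock, state one decisive analysis: the between-arm difference in transplant-free survival at week 12, with death or transplant as the event, a 95% CI and a two-sided 0.05 level. Use the Kaplan-Meier estimate at week 12, or the simple proportion if week-12 status is complete.

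Reconcile the censoring sentence in the discontinuation section with this endpoint, for analysis purposes, and state how onset of liver cancer is handled. Say whether the log-rank concerns overall or transplant-free survival and over what period. Label the full-follow-up log-rank, any other test of week-12 survival and the week-24 results as supportive, with no claim of success from them alone.

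Adjustment for baseline severity is optional. If it is wanted, the covariate and method must be named.

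The cost is one or two sentences in the statistical section, one reconciled sentence elsewhere, and the loss of freedom to choose the test after seeing results. No extra patients or data are needed.

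### Last observation carried forward is the only missing-data rule and does not separate death from dropout, so the week-12 MELD, Child-Pugh and quality-of-life comparisons can reflect mortality rather than function

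*Combined protocol and SAP*

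**What the plan says.** The section Data management and Statistical methods has one sentence on missing data: "The last observation carried forward approach was used for missing values". It is not limited to particular outcomes. It does not distinguish death, transplantation, withdrawal and loss to follow-up, and no sensitivity analysis accompanies it.

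The secondary outcomes at week 12 include "the influence on liver function assessed by MELD score", the same for Child-Pugh, and "quality of life assessed by WHOQOL-BRIEF at week 12". On testing, "Comparison of the two groups is conducted for the continuous variables with" a t-test, and "the categorical variables or rates with the chi-square test". Efficacy is analysed in two sets. The full analysis set (FAS) is randomised patients with at least one dose. The per-protocol set (PPS) is defined by completion: "those who complete all the visits constitute the per-protocol set (PPS".

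For survival, "The Kaplan-Meier overall survival curves will be generated and tested by log-rank". In addition, "Cox proportional hazards regression model will be adopted to determine the prognostic factors associated with transplant-free survival". The primary outcome is week-12 transplant-free survival, but no test is named as primary. The only censoring rule, under Criteria for discontinuing or modifying allocated interventions, covers transplantation and onset of liver cancer. It does not mention loss to follow-up. Attrition of 10% appears only under Sample size.

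**The concern.** A patient who dies before week 12 has no week-12 score. If that score counts as missing, which the text neither says nor excludes, the only stated rule enters the last value before death. Someone who dies soon after entry is then scored near baseline. The PPS does not resolve this: read literally, it drops everyone who died and compares selected survivors. Neither analysis says how death enters the scores.

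Death is common in this population, and the trial is designed to find it unequal between arms. The FAS t-test would mix survivors' function with pre-death values in different proportions, so a difference could not be read as an effect on liver function or quality of life.

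The primary outcome raises a smaller, conditional question. If week-12 status were compared by chi-square with values carried forward, patients lost before week 12 would count as event-free.

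**Working it through.** **Inputs from the documents.** Control 8-week mortality 30.87%; difference 12 points, taken as the planned effect, so 18.87% with herbal medicine; 255 per arm; 10% attrition; power 0.80; two-sided 0.05. **Assumptions.** The 8-week rates stand in for week 12. The SD, the gap between pre-death and survivors' scores, and any unequal loss are not in the documents, so ranges are used.

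**The plan's own figure.** With the control-rate variance in both arms, n = 2 × 0.3087 × 0.6913 × (1.960 + 0.842)² / 0.12² = 232.6. Multiplying by 1.10 gives 255.9; rounding up to 233 and dividing by 0.90 gives 259. The stated 255 is reproduced to within 2%.

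**Scores affected.** Deaths: 255 × 0.3087 = 78.7 and 255 × 0.1887 = 48.1, together 126.8 of 510 (25%). Planned attrition is 25.5 per arm, so death would be the main source of carried-forward scores. Survivors number about 176 and 207.

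**Difference from mortality alone.** Let survivors have mean 0 and SD 1 in both arms, and let pre-death scores be G SD worse. With carry-forward each arm's mean is pG, so the difference is (0.3087 − 0.1887) × G = 0.12G. Each arm's variance is 1 + p(1 − p)G², with p(1 − p) = 0.2134 and 0.1531. For G = 1, SE = √[(1.2134 + 1.1531)/255] = 0.0963, z = 0.12/0.0963 = 1.25, and the rejection probability is about 24%.

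| G (assumed) | Difference, SD | Significant |
|---|---|---|
| 0.5 | 0.06 | about 10% |
| 1 | 0.12 | about 23–24% |
| 2 | 0.24 | about 54% |

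Simulated t-tests agree with these within simulation error.

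**Equal mortality.** With 30.87% in both arms, type I error stays near 5%. A 0.30 SD effect in survivors shows as 0.30 × 0.6913 = 0.21 SD, provided pre-death scores are the same in both arms.

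**Primary outcome, equal 10% loss at entry** (two-proportion normal approximation):
- No loss: power 88.2%.
- Losses censored (229.5 per arm): 84.7%.
- Losses carried forward as event-free: 27.78% vs 16.98%, a difference of 10.8 points, power 83.5%.

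Carrying forward rather than censoring costs 1.2 points. By simulation the cost is about 0.5 if loss is spread over 12 weeks and nil if loss falls in weeks 8 to 12.

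**Primary outcome, unequal loss** (assumed 5% control, 15% herbal medicine; no true effect). At entry, carry-forward gives 0.95 × 30.87 = 29.33% vs 0.85 × 30.87 = 26.24%, and rejects in about 12% of trials. This falls to about 6% with spread loss and 5% with loss in weeks 8 to 12. Censoring holds about 5% only if lost patients carry their arm's average risk. With loss at entry:

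| Lost patients' risk | Carry-forward | Censoring |
|---|---|---|
| near 0 | 5.0% | 13.8% |
| 15% | 6.6% | 7.3% |
| 30.87% | 12.2% | 5.0% |
| 60% | 34.7% | 13.8% |

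**The alternatives, on the same tests.** A composite ranking death worst, with identical survivors and the 12-point mortality difference, favours herbal medicine with probability 0.8113 × 0.3087 + 0.5 × 0.3087 × 0.1887 + 0.5 × 0.6913 × 0.8113 = 0.56. By simulation it rejects in about 66% of trials. With equal mortality and a 0.30 SD survivor effect it detects the effect in about 35%, against about 38 to 60% for carry-forward (lower as G rises) and about 80% for a t-test in survivors.

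Counting losses as events, with no true effect and 5%/15% loss, gives 34.33% vs 41.24% and rejects in about 36% of trials. With a true 12-point effect the difference shrinks to 34.33 − 31.04 = 3.3 points.

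**The case against.** The text does not say that scores after death are missing values, so what is shown is an ambiguity, not an adopted faulty analysis. That is fair, and it limits confidence. The ambiguity still matters, because no other rule governs these patients in the FAS.

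The score magnitudes depend on an assumed gap of 0.5 to 2 SD. That is also fair: 0.12G follows from the plan's own rates, but G does not. A reader might infer that carry-forward inflates type I error for the scores in general. It does not; with equal mortality the error stays near 5%.

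A composite ranking death worst reacts more strongly to mortality than carry-forward does (about 66% against at most 54%) and detects survivor effects less often. This stands. The composite is explicit about death, but it does not isolate liver function or quality of life, so it cannot be offered as a cure.

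On the primary outcome, a reader might infer that the plan will count losses as event-free and so bias the main result. The documents do not support that. Kaplan-Meier, log-rank and Cox methods are planned and would ordinarily censor losses. The FAS needs one dose and most patients stay in hospital for 8 weeks, which makes loss at entry remote. The 5%/15% split is assumed; unequal loss is only possible, since no placebo or patient blinding is described. Nor is censoring always better: it does worse in two of the four lost-patient scenarios.

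**Conclusion.** The point holds for the three week-12 scores, with medium confidence. Under the literal reading, about a quarter of FAS scores would be pre-death values, unequally split by the effect the trial is designed to detect, and the PPS would exclude the same patients. The result could then be significant from mortality alone. How often depends on the assumed gap and on 8-week mortality standing in for week 12.

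For the primary outcome only an omission is established: neither the test nor the handling of losses is stated. Its cost is about 1 power point under the planned attrition if loss is equal. Material bias needs the chi-square-with-carry-forward reading together with early, unequal loss. The sponsor should correct this, but it does not show that the primary result would be invalid.

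**What to change.** Replace the carry-forward rule.

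- **Week-12 scores.** Do not carry pre-death values forward. Analyse patients alive and transplant-free by ANCOVA on the baseline score, with multiple imputation for values missing while alive. Report this beside mortality, labelled as conditional on survival and not a randomised comparison.
- **If one FAS comparison is wanted.** Use a rank composite with death or transplant worst, labelled as survival and function combined and not as an effect on liver function or quality of life. Disclose its rejection rate from mortality alone and its low power for survivor effects.
- **Primary outcome.** Name a Kaplan-Meier-based week-12 comparison (log-rank, or the week-12 difference with a 95% CI), with losses censored at last contact. Add a sensitivity analysis counting losses as events, labelled an extreme bound because it rejects so often under unequal loss. Reconcile the rule that censors at transplantation with the transplant-free survival endpoint.

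The cost is SAP wording and some programming, with no new data. The price is interpretive: the survivors' analysis cannot carry a treatment claim, the composite is harder to read in score points, and censoring is itself biased if loss is related to prognosis.

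### All five secondary outcomes are judged at two-sided P < 0.05 with no multiplicity rule or exploratory label; if all five nulls are true, the chance of at least one significant result is about 13-23%

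*Combined protocol and SAP*

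**What the plan says.** Under Outcome measurements, the plan states a single primary: "The primary outcome is transplant-free survival at week 12". Five numbered secondary outcomes follow, beginning "Secondary outcomes include (1) transplant-free survival at week 24". The second to fourth are MELD score, Child-Pugh score and WHOQOL-BRIEF quality of life, all at week 12. The fifth is "the incidence of serious complications (including infections, encephalopathy, HRS, and gastrointestinal bleeding) from week 1 to week 24".

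Under Data management and Statistical methods, the group comparisons are set out generically. "Comparison of the two groups is conducted for the continuous variables with" a t-test, and categorical variables or rates are compared with chi-square. Survival curves are compared by log-rank. The section ends: "The statistical significance is defined as a two-sided" P < 0.05. That threshold is not tied to any particular outcome.

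Nowhere does the document rank the secondary outcomes, make them conditional on the primary, divide alpha among them, adjust for multiplicity or call them exploratory or descriptive. The only exploratory wording concerns a logistic regression for factors associated with complications, which is not a treatment comparison. The document refers to no separate or later analysis plan that might supply a rule.

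**The concern.** A threshold of 0.05 limits the error of one test. Applied to five outcomes with nothing linking them, it leaves the chance of at least one false positive among them uncontrolled. The statistical section does not say whether a significant MELD, Child-Pugh, quality-of-life or complication result is a confirmatory finding or a lead for later work, nor whether it may be claimed if week-12 survival shows no difference.

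What is at stake is the wording of the trial's conclusions. Under the plan as written, a report could state that CHM significantly improved one of five secondary outcomes, and a reader could not tell from the plan how much weight that P value bears. A rule added after the results are seen could not be shown to be independent of them.

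**Working it through.** **Inputs from the document.**
- Per-test level: 0.05, two-sided (Data management and Statistical methods).
- Listed secondary outcomes: k = 5 (Secondary outcomes).
- Complication types named within the fifth outcome: 4. Tested one by one, they would give 4 + 4 = 8 tests. The plan does not say that they will be.

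**Assumptions not in the document.**
- All secondary nulls are true.
- The test statistics are standard normal with one common correlation r. No correlation is given, so r is varied over 0, 0.5 and 0.8.

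The plan states no family-wise error rate, so there is no figure of its own to reproduce. Its only stated level is 0.05.

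**Step 1: independent tests.** The chance of at least one significant result is 1 - (1 - 0.05)^k.
- Five tests: 1 - 0.95^5 = 1 - 0.774 = 22.6%.
- Eight tests: 1 - 0.95^8 = 1 - 0.663 = 33.7%.
- Five tests, counting only results favouring CHM (0.025 each): 1 - 0.975^5 = 1 - 0.881 = 11.9%.

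**Step 2: correlated tests.** Write each statistic as Z_j = √r·F + √(1 - r)·E_j, with F and the E_j independent standard normal. Given F = f, the tests are independent, so

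P(at least one |Z_j| > 1.96) = 1 - ∫ [Φ((1.96 - √r·f)/√(1 - r)) - Φ((-1.96 - √r·f)/√(1 - r))]^k φ(f) df.

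For results favouring CHM only, the second Φ term is dropped. Numerical integration gives:

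| Family | r = 0 | r = 0.5 | r = 0.8 |
|---|---|---|---|
| Five listed outcomes, two-sided | 22.6% | 18.3% | 12.7% |
| Five listed outcomes, favouring CHM only | 11.9% | 9.1% | 6.4% |
| Four outcomes other than week-24 survival, two-sided | 18.5% | 15.6% | 11.4% |
| Eight tests, if complication types were split, two-sided | 33.7% | 25.0% | 15.7% |

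The third row covers the case in which the survival effect is real but the other four nulls hold. A simulation of 1,000,000 sets of statistics agrees with the two-sided rows for five and eight tests.

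**Step 3: what a rule would do.** Bonferroni over five tests uses 0.05/5 = 0.01 each. If they are independent, the family rate is 1 - 0.99^5 = 4.9%. Holm also keeps it at or below 5%.

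**The case against.** The strongest reply is that this is a common reporting gap with no bearing on the primary inference. Most of that stands. The plan names one primary outcome and calls the rest secondary, which already signals their relative importance. The primary test's error is untouched. Unadjusted secondary analyses are acceptable when labelled exploratory. This plan has no such label, and its one threshold covers every comparison.

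Four stronger readings are tempting, and the documents do not support them.

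- *A rate of 18-25% as a direct consequence of the plan.* Those are the five-test and eight-test results at a correlation of 0.5, which the documents do not give. Correlation might well be substantial: MELD and Child-Pugh share bilirubin and coagulation, and encephalopathy enters both Child-Pugh and the complications outcome. Only a range can be stated.
- *Eight secondary tests.* The fifth outcome is one numbered item that lists four complication types. Separate testing is possible but not specified.
- *A broken promise of 5% across the family.* The plan sets a significance threshold. It does not undertake to hold the family-wise error of the secondary outcomes at 5%.
- *An effectiveness conclusion that cannot stand, or a secondary result that may rescue a failed primary.* No section makes a secondary outcome a criterion of success. The plan does not rule out such a claim, but it does not provide for one.

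The two-sided rate also counts false results against CHM. For a false claim of benefit, the relevant figure is about half as large.

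**Conclusion.** The gap is real and limited to claims made from the secondary outcomes. With all secondary nulls true, the chance of at least one nominally significant result among the five listed outcomes is about 13-23% for a common correlation from 0.8 down to 0. Counting only results in favour of CHM, it is about 6-12%, compared with 2.5% for a single test. The 16-34% range is hypothetical, since it needs the four complication types to be tested separately.

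The rate exceeds the single-test level throughout the range examined, so the direction of the finding does not rest on one chosen correlation. The exact size does rest on the assumed common correlation and on all nulls being true. Analysing efficacy in both the full analysis set and the per-protocol set, with neither named as deciding, adds further opportunities that these figures do not include. The single primary outcome keeps its own 5% error, and nothing here calls that test into question on grounds of multiplicity.

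**What to change.** Replace the last sentence of Data management and Statistical methods with wording to this effect: *Two-sided P < 0.05 is the confirmatory criterion for week-12 transplant-free survival only. All secondary outcomes and other assessed parameters are exploratory; they are reported as estimates with 95% confidence intervals and without claims of significance.*

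If the sponsor wants confirmatory secondary claims, it should instead prespecify a gatekept testing order or a Holm procedure. That route also requires naming the single analysis set that decides and the test used for the primary outcome. The plan offers both analysis sets, and both chi-square and log-rank, without assigning either to the primary, so a gate could open under one analysis and stay closed under another. The choice of order is the sponsor's.

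The change should be made before database lock. It needs no extra patients or data. The cost is that a secondary outcome could no longer be claimed as significant on an isolated P < 0.05.
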